9.6.9 Quality of life

Quality of life will be assessed by the EORTC QLQ-30 questionnaire, included in appendix 6. The 30 questions cover: global health status/QoL, 5 functional scales (physical, role, cognitive, emotional and social), 3 symptom scales (fatigue, nausea/vomiting, pain) and six single items (dyspnoea, insomnia, appetite loss, constipation, diarrhoea, and financial difficulties due to treatment or illness). QoL data will be analyzed by mixed models, assessing changes over time and differences between treatment arms; according to standard statistical methods (details will be provided in a separate appendix). For the purpose of this study, QoL assessment will focus on the following nine scales: global health status/QoL, all five functional scales, two symptom scales (fatigue and pain) and one single items (financial difficulties).

9.6.10 Other secondary endpoints

Other secondary endpoints (CsA-independent hematological response at 24 months, Need for transfusions, Need for any supportive care including hospitalization, safety and tolerability) will be described by standard summary statistics (frequency tables for categorical variables, mean with standard deviations and quantiles for continuous variables).

10. Assessment of Safety

A trial specific Safety Monitoring Plan is included in appendix 5. In this trial, safety will be determined through the collection of Adverse Event (AE) data, laboratory tests, etc.

Timepoints are listed in the flowchart (appendix 3).

The reference safety information (RSI) for Eltrombopag is the SmPC. The RSI for ATGAM is the USPI.

10.1 Definitions of Adverse Events

The EU Clinical Trials Directive 2001/20/EC and the UK Medicines for Human Use (Clinical Trials) Regulations 2004 and Amended Regulations 2006 give the following definitions:

Adverse Event (AE)

Any untoward medical occurrence or effect in a patient treated on a trial protocol, which does not necessarily have a causal relationship with the trial treatment. An AE is therefore described as any unfavourable, noxious and unintended sign (including an abnormal laboratory finding), symptom or disease temporally associated with the use of the trial treatment but also from medication error and use of a medicinal product outside of the terms of marketing authorisation (including misuse and abuse), whether or not related to the trial treatment.

Adverse Reaction (AR)

Any untoward, noxious and unintended response to a trial treatment but also from medication error and uses outside the terms of marketing authorisation (including misuse/abuse of medicinal product) related to any dose administered. A causal relationship between the trial treatment (or medication error, misuse/abuse of medicinal product) and an adverse event is at least a reasonable possibility, i.e. the relationship cannot be ruled out.

Serious Adverse Event (SAE)

Any untoward medical occurrence or effect in a patient treated on a trial protocol which does not necessarily have a causal relationship with the trial treatment (or medication error, misuse/abuse of medicinal product), that also, at any dose:

- Results in death
- Is life threatening
- Is a secondary cancer
- Results in persistent or significant disability/incapacity
- Requires in-patient hospitalisation or prolongs existing hospitalisation
- Results in congenital anomaly or birth defect
- Is otherwise medically significant (i.e. all accidental or intentional overdoses whether they result in an adverse event or not, or any event which the investigator considers significant but which is not covered by the above)

Suspected Serious Adverse Reaction (SSAR)

This is defined as an adverse reaction, the nature or severity of which is consistent with the known trial treatment information (e.g. Summary of Medicinal Product Characteristics (SmPC), Investigator's Brochure (IB) or Investigator Medicinal Product Dossier (IMPD)).

Suspected Unexpected Serious Adverse Reaction (SUSAR)

This is defined as an adverse reaction, the nature or severity of which is not consistent with the known trial treatment information.

A serious event or reaction is not defined as a SUSAR when:

- it is serious but expected
- it does not fit the definition of an SAE, whether expected or not

10.2 Procedures for Adverse Event Reporting

10.2.1 All Adverse Events

All adverse events that occur between the first trial-related procedure (i.e. screening) until the last follow up visit (or after this date if the investigator feels the event is related to the trial treatment) must be recorded. Those meeting the definition of a serious adverse event (SAE) must be reported using the SAE Report form.

Investigators must record in the Case Report Form (CRF) and the patient notes their opinion concerning details of nature, onset, duration, severity of the SAE and assess any relationship to the investigational medicinal product. Medical terminology and medical diagnosis should always be used to describe any event. Investigators should avoid vague terms such as "sick".

10.2.1.1 Adverse Event Term

The PI (or delegate) must provide an adverse event term (preferred diagnosis as AE term, not symptoms) for each adverse event, preferably using the Short Name as listed in the Common Terminology Criteria for Adverse Events v4.03.0 (CTCAE), available online at: <http://ctep.cancer.gov> or http://evs.nci.nih.gov/ftp1/CTCAE/CTCAE_4.03_2010-06-14_QuickReference_8.5x11.pdf.

10.2.1.2 Severity

Severity for each adverse event, including any lab abnormality, will be determined by the PI using the Common Terminology Criteria for Adverse Events v4.03 (CTCAE) as a guideline, wherever possible. In those cases where the CTCAE criteria do not apply and where there is no accepted alternative grading system e.g. Bearman Scale, severity should be defined according to the following criteria:

Mild	Awareness of sign or symptom, but easily tolerated
Moderate	Discomfort enough to cause interference with normal daily activities
Severe	Inability to perform normal daily activities
	Life threatening: Immediate risk of death from the reaction as it occurred.

10.2.1.3 Causality

Relationship to trial treatment will be determined by the PI as follows:

Not Related	
No relationship between the experience and the administration of the trial treatment; related to other etiologies such as concomitant medications or patient's clinical state.
 
The current state of knowledge indicates that the relationship is unlikely

Related	
A reaction that follows a plausible temporal sequence from administration of the trial treatment and follows a known response pattern to the suspected treatment. The reaction might also have been produced by the patient's clinical state or other modes of therapy administered to the patient.
 
A reaction that follows a plausible temporal sequence from administration of the trial treatment and follows a known response pattern to the suspected treatment. The reaction cannot be reasonably explained by the known characteristics of the patient's clinical state or other modes of therapy administered to the patient.
 
An adverse event, which is listed as a possible adverse reaction and cannot be reasonably explained by an alternative explanation, e.g., concomitant drug(s), concomitant disease(s).

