10.2.1.4 Expectedness

An expectedness assessment needs to be conducted for all SAEs by the Sponsor (EBMT CTO) using the SmPC which is the Reference Safety Information (RSI) of eltrombopag and recorded appropriately on the SAE Report form. The RSI is to be used for the purposes of determining expectedness and thus SAE/SUSAR reporting. Expectedness of the event listed in section 4.8 of the RSI within the SmPC, to the investigational medicinal product will be determined as follows:

Expected	
The event is listed in the RSI (SmPC) or the trial protocol as expected with the trial treatment or is commonly seen in clinical experience (patient population, dosage)

Unexpected	
The event is not listed in the RSI (SmPC) or in the trial protocol, or the severity of the event is greater than that listed in the RSI (SmPC) or the trial protocol (e.g. mild nausea is listed as expected in the RSI (trial protocol but the event is moderate or severe nausea).
 
In assigning expectedness, characteristics of the disease should be taken into account.

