10.2.2 Reporting of Serious Adverse Events (SAE)

As Sponsor, the EBMT is responsible for pharmacovigilance. Events defined as serious must be reported by fax to the EBMT CTO using the SAE Report form, **within 24 hours** of

observing or learning of the event. If a copy of the SAE Report form is required, this can be obtained from the Clinical Trial Coordinator.

The following attributes must be assigned when reporting:

- Detailed description of the event
- Adverse event term (see Adverse Event Term section for details 10.2.1.1)
- Seriousness criterion
- Date of onset and outcome
- Severity of the event (see Severity section for details 10.2.1.2)
- Assessment of relatedness to the protocol treatment (see Causality section for definitions 10.2.1.3) and action taken
- Assessment of expectedness for the protocol treatment (see section 10.2.1.4)
- Other suspect concomitant drugs or devices

All SAEs regardless of relationship to investigational product will be collected from the time of informed consent until the end of the end of follow-up period. All SAEs regardless of causality will be collected until the end of the follow-up period.

All SAEs will be followed up until resolution. The investigator will be asked to provide interim and follow-up reports, as necessary, if the SAE has not resolved at the time of initial report.

All deaths occurring on trial must be reported as a SAE in the patient's notes, as an outcome on the SAE form and on the CRFs sent to the EBMT CTO. For all deaths, available autopsy reports (or death certificate if available) should be sent with the notification.

Please note death is the outcome of an SAE it cannot be the AE term.

ALL SAE's must be assessed and signed by the Principal or a Co-Investigator (this must be recorded on the staff delegation log).

Any SAE brought to the investigator's attention after the patient has completed the study and considered by the investigator as possibly related to IMP must be reported to the EBMT CTO during the trial duration.

It will be left to the investigator's clinical judgment whether or not an adverse event is of sufficient severity to require that the patients should be removed from the treatment. A patient may also voluntarily withdraw from treatment due to what they perceive as an intolerable adverse event. If either of these occurs, it must be made clear if the patient is being withdrawn from the trial or just the trial medication is being stopped.

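### The *Related* category in 10.2.1.3 admits only known or listed reactions, contrary to the adverse-reaction test in 10.1, so a SUSAR wholly new in nature could be missed or delayed

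*Protocol*

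**What the plan says.** Section 10.2.1.3 gives the PI two categories, *Not Related* and *Related*.

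- *Related* has three descriptions. The first two share the opening "A reaction that follows a plausible temporal sequence from administration of the trial treatment and follows a known response pattern to the suspected treatment" and differ only in whether the patient's condition or other therapy might also explain the event. The third is "An adverse event, which is listed as a possible adverse reaction and cannot be reasonably explained by an alternative explanation".
- *Not Related* has two descriptions. One is that there is no relationship and the event is attributed to another etiology. The other is "The current state of knowledge indicates that the relationship is unlikely".

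Section 10.1 defines an adverse reaction differently: a causal relationship "is at least a reasonable possibility, i.e. the relationship cannot be ruled out". Its SUSAR definition builds on that one: "This is defined as an adverse reaction, the nature or severity of which is not consistent with the known trial treatment information".

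Section 10.2.2 fixes which text is used on the SAE form. Among the required attributes is "Assessment of relatedness to the protocol treatment (see Causality section for definitions 10.2.1.3) and action taken". It also states that "ALL SAE's must be assessed and signed by the Principal or a Co-Investigator". Section 10.2.1.4 gives the sponsor the expectedness assessment for all SAEs. Section 10.3 sets the expedited deadlines at 7 calendar days for fatal or life-threatening SUSARs and 15 calendar days for the others.

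**The concern.** A SUSAR has to pass two separate tests: it must be related, and it must be unexpected. Whether a reaction is already known or listed belongs to the second. Section 10.2.1.3 brings it into the first. For a reaction new in nature, the novelty that makes it unexpected also prevents it from meeting any description of *Related*.

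The wide definition in 10.1 does not help an investigator who follows the instructions, because 10.2.2 points to the table and not to 10.1. With only two categories available, such an event could be rated *Not Related* simply because nothing is known about it, and the expedited report might then not be triggered.

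This matters somewhat more here than in a trial of a well-established regimen, because section 8.6.3 says the potential for interaction between eltrombopag and cyclosporine A is unknown.

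**Working it through.** No arithmetic applies. The check sets the five descriptions in 10.2.1.3 against the definitions in 10.1 for three kinds of serious event, each with plausible timing and no other evident cause.

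**Requirements**

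- *Related* 1 and 2: plausible timing and a known response pattern.
- *Related* 3: already listed, with no reasonable alternative explanation.
- *Not Related* 1: no relationship; another etiology.
- *Not Related* 2: current knowledge makes the link unlikely.
- Adverse reaction (10.1): a reasonable possibility that cannot be ruled out. Neither a known pattern nor a listing is required.
- SUSAR (10.1): an adverse reaction, with nature or severity not consistent with known information.

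All 3 of the 3 *Related* descriptions therefore need prior knowledge: 2 need a known pattern and 1 needs a listing.

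**Test cases**

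| Serious event | Can be rated *Related*? | Fits *Not Related*? | Adverse reaction under 10.1? |
|---|---|---|---|
| Listed reaction, more severe than listed | Yes | No | Yes |
| Unlisted, but follows a known response pattern | Yes | No | Yes |
| Wholly new in nature | No (0 of 3) | No (0 of 2) | Yes |

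In the third row, *Related* 1 and 2 fail on the known pattern and *Related* 3 fails on the listing. *Not Related* fails as well: no other etiology is present, and an absence of knowledge is not knowledge that a link is unlikely. Yet the event meets 10.1, is unexpected under 10.2.1.4 because it is unlisted, and so is a SUSAR.

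Of the two routes to a SUSAR, severity stays open. Nature stays open only for an unlisted event that follows a known pattern, and is closed for a wholly new reaction.

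**Could another step correct the rating?**

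1. Sponsor assessment of every SAE (10.2.1.4): described as expectedness. Section 10.3 likewise gives expectedness as the reason for immediate SAE reporting.
2. Forwarding of SAEs to the two companies' pharmacovigilance departments (10.2.2 and Appendix 5): described as forwarding, with requests for more information.
3. Quarterly toxicity information to the eltrombopag manufacturer (18.1).
4. Six-monthly AE and SAE listings to the IDMC (15.1.1 and Appendix 5).

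None of the 4 is described as a review of the investigator's causality rating. The third and fourth also run on cycles much longer than 7 or 15 days.

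**The case against.** The strongest reply is that the governing definition is already right. A SUSAR is defined through the adverse-reaction test in 10.1, and the sponsor is responsible for pharmacovigilance, so a sponsor applying its own definition would use the wide test. Other text supports that reading: 10.2.1.4 counts unlisted events as unexpected, and 10.2.2 asks for post-study SAEs that are possibly related.

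The wholly new reaction also fits *Not Related* no better than *Related*. An investigator might raise a query or choose *Related*, and nothing makes *Not Related* the default. The exemptions in 10.2.3 cover named or already described events, so a new reaction would ordinarily reach the sponsor within 24 hours with a full description. Finally, the absence of a causality review is inferred from silence: section 10.5, the SAE form and the agreements with the companies were not available to check.

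Much of this stands and limits the point. Receipt of the SAE is not in doubt, and an attentive sponsor or investigator could reach the right answer. What does not stand is the idea that the text is therefore adequate. The investigator is directed to a table that contradicts 10.1, and no section available assigns anyone to correct the result. A legal reporting duty should not depend on readers setting aside the definition they are told to use.

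**Conclusion.** The point holds. The definition of *Related* in 10.2.1.3 contradicts the protocol's own definition of an adverse reaction, and 10.2.2 makes the narrower one operative for SAE reports. A serious reaction wholly new in nature cannot literally be rated *Related*, so its 7- or 15-day report could be missed or delayed.

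The effect is confined to that class of event. What is at risk is its classification and expedited reporting, not the sponsor's knowledge that it occurred. Efficacy results and the between-arm safety comparison are not affected. The number of SAEs involved and the length of any delay cannot be derived from the protocol.

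The conclusion assumes that investigators apply the table as written and that no document outside the available text provides a sponsor causality review. It should be fixed because it concerns patient safety and the correction is simple.

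**What to change.** In 10.2.1.3, replace the three *Related* descriptions with the test in 10.1: there is at least a reasonable possibility that the trial treatment caused the event, meaning the relationship cannot be ruled out, whether or not the reaction is known or listed. Leave known and listed to the expectedness assessment in 10.2.1.4. Align the SAE form guidance and site training.

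Then re-check any SAE rated *Not Related* solely because it was not a recognised reaction. The protocol does not show whether any exist.

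The cost is a wording change to one table, the matching guidance and training, and a short review of SAEs already rated *Not Related*. The downside is that somewhat more events will be classed as related and reported.

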10.2.1.4 Expectedness

An expectedness assessment needs to be conducted for all SAEs by the Sponsor (EBMT CTO) using the SmPC which is the Reference Safety Information (RSI) of eltrombopag and recorded appropriately on the SAE Report form. The RSI is to be used for the purposes of determining expectedness and thus SAE/SUSAR reporting. Expectedness of the event listed in section 4.8 of the RSI within the SmPC, to the investigational medicinal product will be determined as follows:

Expected	
The event is listed in the RSI (SmPC) or the trial protocol as expected with the trial treatment or is commonly seen in clinical experience (patient population, dosage)

Unexpected	
The event is not listed in the RSI (SmPC) or in the trial protocol, or the severity of the event is greater than that listed in the RSI (SmPC) or the trial protocol (e.g. mild nausea is listed as expected in the RSI (trial protocol but the event is moderate or severe nausea).
 
In assigning expectedness, characteristics of the disease should be taken into account.

10.2.2 Reporting of Serious Adverse Events (SAE)

As Sponsor, the EBMT is responsible for pharmacovigilance. Events defined as serious must be reported by fax to the EBMT CTO using the SAE Report form, **within 24 hours** of

observing or learning of the event. If a copy of the SAE Report form is required, this can be obtained from the Clinical Trial Coordinator.

The following attributes must be assigned when reporting:

- Detailed description of the event
- Adverse event term (see Adverse Event Term section for details 10.2.1.1)
- Seriousness criterion
- Date of onset and outcome
- Severity of the event (see Severity section for details 10.2.1.2)
- Assessment of relatedness to the protocol treatment (see Causality section for definitions 10.2.1.3) and action taken
- Assessment of expectedness for the protocol treatment (see section 10.2.1.4)
- Other suspect concomitant drugs or devices

All SAEs regardless of relationship to investigational product will be collected from the time of informed consent until the end of the end of follow-up period. All SAEs regardless of causality will be collected until the end of the follow-up period.

All SAEs will be followed up until resolution. The investigator will be asked to provide interim and follow-up reports, as necessary, if the SAE has not resolved at the time of initial report.

All deaths occurring on trial must be reported as a SAE in the patient's notes, as an outcome on the SAE form and on the CRFs sent to the EBMT CTO. For all deaths, available autopsy reports (or death certificate if available) should be sent with the notification.

Please note death is the outcome of an SAE it cannot be the AE term.

ALL SAE's must be assessed and signed by the Principal or a Co-Investigator (this must be recorded on the staff delegation log).

Any SAE brought to the investigator's attention after the patient has completed the study and considered by the investigator as possibly related to IMP must be reported to the EBMT CTO during the trial duration.

It will be left to the investigator's clinical judgment whether or not an adverse event is of sufficient severity to require that the patients should be removed from the treatment. A patient may also voluntarily withdraw from treatment due to what they perceive as an intolerable adverse event. If either of these occurs, it must be made clear if the patient is being withdrawn from the trial or just the trial medication is being stopped.

10.2.3 Expected adverse events

The following adverse events, for the purposes of the trial, will be considered as expected events that are disease/transplant related and do not require immediate reporting as an SAE:

- Infectious events which do not require intensive care unit support
- Bleeding which did not require red blood cell transfusion
- Clonal evolution (as defined 9.5)
- Some adverse events have been previously reported or anticipated during the use of eltrombopag; they are described in paragraph 8.3.1.

These events must still be recorded on the trial CRFs as AEs.

10.3 Expedited reporting of SUSAR

As of May 1st 2004, the sponsors of clinical trials conducted in the EU and EEA must ensure that all relevant information regarding suspected unexpected serious adverse reactions (SUSARs) are recorded and reported in an expedited fashion.

It is a legal requirement of the sponsor to report fatal or life-threatening SUSARs **within 7 calendar days** to the relevant Regulatory Authorities and the European Medicines Agency
RACE Protocol version 3.1, 02-Aug-2016

after receiving first notification of the event. Non-fatal and non life-threatening SUSARs must be reported to the Regulatory Authorities and the European Medicines Agency **within 15 calendar days**. The EBMT CTO will have the responsibility for reporting such events to Ethics Committees, all applicable Regulatory Authorities and site principal investigators as well.

Therefore, all SAEs must be immediately reported to the CTO, to allow time for the expectedness assessment.

